9.3 Seroquel XR utilisation

At the time of initiation of Seroquel XR, the diagnosis for which Seroquel XR was prescribed, whether the patient was experiencing psychotic symptoms, Clinical Global Impression, the initial daily dose of Seroquel XR prescribed and any concomitant antidepressant drug(s) and dose(s) prescribed will be summarized descriptively by country and overall.

The last prescribed daily dose prior to the index date, the maximum daily dose prescribed, modal daily dose, and the duration for each dose of Seroquel XR as prescribed will be summarized descriptively by country and overall.

Doses described above will be summarized in two ways.

- As continuous variable: the following will be calculated: number mean, mode, median, minimum, maximum, and standard deviation
- As a categorical variable: number and % of patients will be provided for each of the following dose levels: 50 mg, 100 mg, 150 mg, 300 mg and other.

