2.1 Overall study design

This is a multinational, multicenter, retrospective, observational study of antidepressant drug utilisation among an inception cohort of patients under specialists (psychiatrists) care who are prescribed Seroquel XR for treatment of major depressive episodes associated with MDD following launch of the indication in each country. The study will be conducted in 5 European countries: Germany, Italy, Romania, Spain, and Sweden to ensure geographic representation across European member states. The sponsor may include alternate EU country(ies) based upon limited use of Seroquel XR for MDD in the countries listed and whose selection will maintain geographic representation among EU countries.

The inception cohort is defined as patients initiating Seroquel XR (as add-on therapy or as monotherapy) during a 9 month period corresponding to 3 to 12 months following the launch of the product in each country for the MDD indication. In the period immediately after launch, physicians may not be aware of the approval of Seroquel XR for add-on treatment for MDD. Therefore, patients treated with Seroquel XR within the 3 months after launch will not be included in the inception cohort because they are not likely to be representative of patients

[figure not shown]
treated in subsequent periods. A drug utilisation questionnaire will be used to collect study data. Data collection will be initiated following a study-defined index date, approximately 12 months after product launch. All study sites within a country will be assigned the same index date and will not be contacted prior to the index date.* Initiation of site-specific activities for selection of patient records meeting study selection criteria will commence on or following the index date. Data on drug utilisation will be censored on the index date. This approach will ensure that study procedures do not influence prescribing practices.

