3.3.1 Inclusion Criteria for Patients

1. Provision of informed consent before initiation of any collection of questionnaire data.
2. Female and male aged 18 years and over.
3. Documented clinical diagnosis of Major Depressive Disorder, Single Episode, or Recurrent.
4. Initiation of Seroquel XR for treatment of MDD during the period defining the inception cohort, i.e. from 3 months after launch until the index date.

The prescription of the medicinal product is clearly separated from the decision to include the patients in the study.

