4.2 Questionnaire Administration

4.2.1 Timeline for questionnaire administration

The exact index date for each country will be selected to optimise preparations leading to completion of drug utilisation questionnaires at all sites within a country following Good Pharmacoepidemiology Practices (PDS 2008).

Contact with investigators and site preparatory activities are initiated following the index date, which will correspond to a date approximately 12 months following the launch of Seroquel XR for MDD in each country.

Preparatory activities for completion of the drug utilisation questionnaires at each site will rely on automated and manual review of data from patient medical records in order to identify patients meeting study inclusion criteria. This selection includes consideration of the inception cohort definition (i.e., initiation of treatment with Seroquel XR in the time interval 3 months after launch up to the index date).

Once site preparatory activities are concluded, including the obtaining of informed consent from the patient, data abstraction of patient medical records using the drug utilisation questionnaire will begin.

Information on the Physician questionnaire related to physician characteristics will be completed based upon the best available recollection by the investigator. Patient questionnaire data will be abstracted from the medical records of the patients maintained at the official location for storage of records for the site/investigator and will be performed by a representative of AstraZeneca.

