9. ANALYSIS

Data obtained from the drug utilisation questionnaire will be reported descriptively. No statistical comparison will be conducted. Summary statistics will be provided. There will be no imputation for any missing values. For continuous variables, the number of responses, mean, median, minimum, maximum, and standard deviation will be provided. For discrete variables, the number of responses and proportion represented by each category will be summarized. Prescribing practices and drug utilisation data will be reported by country permitting comparisons across countries.

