9.4 Other drug utilisation for MDD

The following will be summarized for treatments other than Seroquel XR for MDD the daily dose at the first initiation, whether a dose change accompanied initiation of Seroquel XR, latest dose following Seroquel XR initiation, interval from initiation of Seroquel XR to latest dose change and whether the prescription was continuing on the index date.

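### Section 9.3 summarises the duration of each Seroquel XR dose by plain mean, median and SD although follow-up is cut off at the index date after about 0 to 9 months, so duration is generally understated, by an amount that depends on each country's uptake.

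*Protocol*

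**What the plan says.** Protocol section 2.1 defines the inception cohort as patients who start Seroquel XR "during a 9 month period corresponding to 3 to 12 months following the launch of the product in each country for the MDD indication". Inclusion criterion 4 in section 3.3.1 puts the same window as "from 3 months after launch until the index date". Section 4.2.1 describes the index date as one "which will correspond to a date approximately 12 months following the launch of Seroquel XR for MDD in each country". Section 2.1 adds: "Data on drug utilisation will be censored on the index date". No minimum follow-up is required.

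For the analysis, section 9 states: "For continuous variables, the number of responses, mean, median, minimum, maximum, and standard deviation will be provided", and "There will be no imputation for any missing values". Section 9.3 lists last, maximum and modal daily dose, and says that "the duration for each dose of Seroquel XR as prescribed will be summarized descriptively by country and overall".

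For treatments other than Seroquel XR, section 9.4 reports whether the prescription was continuing on the index date, and the "interval from initiation of Seroquel XR to latest dose change". Section 9.3 has no matching continuation item for Seroquel XR. The form does collect it: in Appendix B (MDD Treatment), Seroquel XR is entered in the concurrent-treatment table, whose end-date column carries a box for still being prescribed at the index date.

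**The concern.** The protocol recognises censoring in its design section but drops it in its analysis section. A patient who starts late has little time in which a dose can run its course. For any patient still on treatment, the dose in force at the index date has a known minimum duration but not a known duration. A plain mean or median treats that minimum as the final value.

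This bears on a stated objective. Section 1.1 sets out to describe differences in treatment practice between countries, and section 9 reports by country so that countries can be compared. Launch and index dates are country-specific. If uptake climbs late in one country and early in another, follow-up differs, and so will the reported durations, even where prescribing is the same.

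Maximum and modal dose are also read over follow-up of unequal length. The effect on them is different in kind and is treated separately below.

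**Working it through.** **Inputs from the protocol.** Starts are allowed over 9 months, from month 3 to month 12 after launch (sections 2.1 and 3.3.1). The index date is about month 12 (section 4.2.1), and utilisation is censored there (section 2.1). Potential follow-up C therefore lies between about 0 and 12 − 3 = 9 months. The protocol gives no figure for treatment duration, uptake or titration, so there is none to reproduce on this point.

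**Assumptions, for illustration only.** Total time on treatment T is exponential with mean m. Starts are uniform over the 9 months, so C is uniform on (0, 9). The recorded duration is X = min(T, C). This models total treatment time, not the per-dose variable that section 9.3 names.

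**Formulas.**
- P(X > t) = exp(−t/m)(1 − t/9)
- Plain mean: E[X] = m − (m²/9)(1 − exp(−9/m))
- Share censored: (m/9)(1 − exp(−9/m))
- Plain median: the t that solves exp(−t/m)(1 − t/9) = 0.5

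The proportional shortfall of the mean, 1 − E[X]/m, equals the share censored. For m = 6: exp(−1.5) = 0.223, so E[X] = 6 − 4 × 0.777 = 2.89 months, and the share censored is (6/9) × 0.777 = 52%.

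| True mean (months) | Plain mean | Shortfall = share censored | True median | Plain median |
|---|---|---|---|---|
| 2 | 1.56 | 22% | 1.39 | 1.12 |
| 3 | 2.05 | 32% | 2.08 | 1.52 |
| 6 | 2.89 | 52% | 4.16 | 2.35 |
| 12 | 3.56 | 70% | 8.32 | 3.15 |
| 24 | 3.99 | 83% | 16.64 | 3.74 |

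However long treatment lasts, X cannot exceed C, so under uniform uptake the plain mean cannot exceed 9/2 = 4.5 months.

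**Dependence on uptake.** Hold prescribing fixed at a true median of 6 months and change only the uptake curve, replacing 1 − t/9 by P(C > t):
- linearly rising uptake, (1 − t/9)²: plain median 1.9 months
- uniform uptake, 1 − t/9: 2.8 months
- linearly falling uptake, 1 − (t/9)²: 4.0 months

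Uptake alone gives about a twofold difference (4.0/1.9) between two countries that prescribe identically.

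**What a censoring-aware summary targets.** Kaplan-Meier with the index date as the censoring time estimates the true median where it lies inside 9 months, for example 4.16 or 8.32 months at m = 6 or 12. The mean restricted to 9 months, m(1 − exp(−9/m)), is 4.66 and 6.33 months in those cases, against plain means of 2.89 and 3.56.

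**Dose variables.** The maximum over a shortened period cannot exceed the maximum over the whole period. Illustrative dose paths were simulated with mean duration 6 months and 200,000 patients:
- Rising path (50, 150, 300 mg): the mean maximum dose fell from 253 to 228 mg, and the mean modal dose from 225 to 190 mg.
- Falling path (300, 150, 50 mg): the maximum was unchanged, and the mean modal dose rose from 174 to 216 mg.
- Constant dose: neither changed.

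**The case against.** The strongest objection is that the model above is not the planned variable. Section 9.3 summarises the duration of each dose as prescribed, and Appendix B records the days supply of every prescription. Dose periods that ended before the index date are complete. A 30-day prescription issued days before the index date may be entered as 30 days, since nothing on the form truncates it. This stands as a limit on the size: the percentages illustrate total treatment time, and days supply could offset part of the cut-off. It does not remove the problem. Days supply stops at the last prescription recorded, so the current dose of a patient who remains on treatment is still incomplete.

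Secondly, the results are descriptive, with no statistical comparison planned, and they validly describe use up to a stated date. That is fair, and the error arises when the figures are read as completed durations. But the protocol itself invites comparison across countries, and section 9.3 gives the reader neither the share continuing nor the length of follow-up. That uptake differs between countries is an assumption; the protocol does not show it.

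Thirdly, an analysis plan that is not shown may add a better summary. It may, but the protocol names the statistics to be used, and they do not suit durations that it calls censored.

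A reader might also infer that all the dose summaries are biased downward. The documents do not support that. They give no titration pattern, modal dose has no fixed direction of bias, and maximum dose is lowered only where the dose would have risen after the index date. Initial dose and last dose before the index date are defined without reference to complete follow-up and are not affected.

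**Conclusion.** The point holds for duration. With follow-up of about 0 to 9 months and plain summaries, dose periods and treatment still running at the index date are counted as complete. Duration is generally understated, to an extent that depends on each country's uptake.

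The size cannot be derived from the protocol. The range of 22% to 83% for true means of 2 to 24 months, and the ceiling of 4.5 months, rest on uniform uptake, exponential duration, a strict cut-off at the index date, and total treatment time in place of duration per dose. The twofold difference between countries rests further on assumed linear uptake curves.

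For dose the conclusion is narrower: maximum and modal dose depend on unequal follow-up and should be labelled and shown accordingly. It would go too far to say that the study's results mainly reflect the observation window. Section 5 names the proportion on a given daily dose as being of particular interest, and for initial and last dose that proportion is sound as defined.

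**What to change.** In section 9.3:

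- Estimate time on Seroquel XR, and time from initiation to first dose change, by Kaplan-Meier from the start and end dates on the form, censoring patients marked as still prescribed at the index date. State how stopping without a prior dose change is handled in the second analysis.
- Where the median is not reached within 9 months, report the proportion continuing at fixed times or the restricted mean.
- Report by country the percentage still prescribed Seroquel XR at the index date, and the potential follow-up (index date minus start date).
- Label maximum and modal dose as values up to the index date, and show them by length of follow-up.
- If days supply is still summarised per dose, state whether supply that runs past the index date is truncated.

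Dose at fixed times since initiation, or a subset with a minimum follow-up, would be optional additions.

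The cost is small: a change of analysis wording and a few more tables, with no new data collection. All of it is descriptive, so it is consistent with section 9 planning no statistical comparison. The remaining limit is that medians beyond 9 months cannot be estimated. With an exponential true median of 12 months, for instance, exp(−9 ln 2/12) = 59% would still be on treatment at 9 months.

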5. SAMPLE SIZE AND PRECISION

Data will be collected from a total of 100-400 patients per country. As a questionnaire will be used to collect the data, the precision around responses is further discussed.

The proportion of patients prescribed a specified daily dose of Seroquel XR is of particular interest. The [PHARMO Report](#) (Institute for Drug Outcomes Research) Part 1 described the distribution of doses of Seroquel XR prescribed to individuals in the Netherlands. The proportion of patients taking Seroquel XR at various dose levels varied from 1% to 67%. The 95% confidence interval for the estimate of a proportion can be calculated for a general situation (i.e., and as applied in this study, the proportion of patients receiving a given dose of Seroquel XR in the sample from each country); for sample sizes of 100, 200, 300 and 400 is provided in [Table 2](#).

Sample sizes of 100-400 patients will provide reasonable precision for a wide range of the estimated proportions of patients receiving a given dose of Seroquel XR in a given country.

Table 2 Precision of Estimated Proportions for a Sample Size of 100 to 400 (2-sided 95% Confidence Intervals)

Estimated Proportion	Sample size = 100	Sample size = 200	Sample size = 300	Sample size = 400
6%	(1.3%,10.7%)	(2.7%,9.3%)	(3.3%,8.7%)	(3.7%,8.3%)
11%	(4.9%,17.1%)	(6.7%,15.3%)	(7.5%,14.5%)	(7.9%,14.1%)
16%	(8.8%,23.2%)	(10.9%,21.1%)	(11.9%,20.1%)	(12.4%,19.6%)
21%	(13%,29%)	(15.4%,26.6%)	(16.4%,25.6%)	(17%,25%)
26%	(17.4%,34.6%)	(19.9%,32.1%)	(21%,31%)	(21.7%,30.3%)

31%	(21.9%,40.1%)	(24.6%,37.4%)	(25.8%,36.2%)	(26.5%,35.5%)
36%	(26.6%,45.4%)	(29.3%,42.7%)	(30.6%,41.4%)	(31.3%,40.7%)
41%	(31.4%,50.6%)	(34.2%,47.8%)	(35.4%,46.6%)	(36.2%,45.8%)
46%	(36.2%,55.8%)	(39.1%,52.9%)	(40.4%,51.6%)	(41.1%,50.9%)
51%	(41.2%,60.8%)	(44.1%,57.9%)	(45.3%,56.7%)	(46.1%,55.9%)
56%	(46.3%,65.7%)	(49.1%,62.9%)	(50.4%,61.6%)	(51.1%,60.9%)
61%	(51.4%,70.6%)	(54.2%,67.8%)	(55.5%,66.5%)	(56.2%,65.8%)
66%	(56.7%,75.3%)	(59.4%,72.6%)	(60.6%,71.4%)	(61.4%,70.6%)
71%	(62.1%,79.9%)	(64.7%,77.3%)	(65.9%,76.1%)	(66.6%,75.4%)
76%	(67.6%,84.4%)	(70.1%,81.9%)	(71.2%,80.8%)	(71.8%,80.2%)
81%	(73.3%,88.7%)	(75.6%,86.4%)	(76.6%,85.4%)	(77.2%,84.8%)

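### Section 9.3 reports Seroquel XR dose as 50, 100, 150, 300 mg and 'other', so the planned summaries do not in general give the proportion at 200 mg, at 250 mg or above 300 mg, although these doses are recorded

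*Protocol*

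**What the plan says.** Section 9.3 of the protocol covers the initial dose, the last dose before the index date, the maximum dose and the modal dose, by country and overall. "Doses described above will be summarized in two ways". The first is "As continuous variable: the following will be calculated: number mean, mode, median, minimum, maximum, and standard deviation". The second is the number and percentage of patients "for each of the following dose levels: 50 mg, 100 mg, 150 mg, 300 mg and other".

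The dosage table in Appendix B has a pre-printed row for each of 50, 100, 150, 200, 250 and 300 mg/day, then three free-entry rows in which the mg/day value is written. The concurrent-treatment table in the same appendix records each Seroquel XR dose change as its own dated line with the exact dose.

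Section 5 states: "The proportion of patients prescribed a specified daily dose of Seroquel XR is of particular interest". It then gives Table 2, the precision of such a proportion for 100 to 400 patients per country. Section 1.1 makes differences between countries in treatment practice an objective. Section 9 rules out statistical comparison, so the by-country tables are where those differences are to be seen.

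**The concern.** 'Other' has two meanings in one protocol. On the form's dosage table it excludes 200 and 250 mg; in the analysis it includes them. Six named doses are collected and four are reported. The two that drop out fall between reported levels and join every dose above 300 mg and any odd value.

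This bears on the quantity that Section 5 picks out. A reader of the planned tables would see what share of a country's patients is at 150 mg or 300 mg, but not at 200 mg, at 250 mg or above 300 mg. In a purely descriptive study these tables are the result, so a country difference inside 'other' may not be visible.

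**Working it through.** **1. The plan's own figures.** Table 2 uses p ± 1.96 × √(p(1 − p)/n). For p = 21%, n = 100: 1.96 × √(0.21 × 0.79/100) = 8.0 points, giving 13% to 29% as printed. For n = 400 the half-width is 4.0 points, giving 17% to 25% as printed. All 64 cells reproduce to the printed rounding. Table 2 is not in question here.

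**2. The two dose lists.**

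| Source | 50 | 100 | 150 | 200 | 250 | 300 | Remaining doses |
|---|---|---|---|---|---|---|---|
| Appendix B dosage table | row | row | row | row | row | row | three free-entry rows, value recorded |
| Section 9.3 categories | yes | yes | yes | other | other | yes | other |

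**3. What the other planned statistics reveal about 'other'.** The named categories have known doses and counts. From the country's n, mean and SD one can therefore back out three facts about 'other': its count, its sum of doses and its sum of squared doses. The maximum adds whether anyone exceeded 300 mg. If 'other' contains 200 mg, 250 mg and two or more higher doses, there are at least four unknown counts and only three equations, so the split is not determined in general.

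**4. A worked case.** The data are invented, because the protocol gives no share by dose. Countries A and B have 100 patients each. Both have 25 at 50 mg, 10 at 100 mg, 26 at 150 mg, 20 at 300 mg and 19 in 'other'.

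- A, 'other': 6 at 200, 12 at 350, 1 at 450 mg.
- B, 'other': 12 at 250, 6 at 400, 1 at 450 mg.

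Sum of doses in the named categories: 25×50 + 10×100 + 26×150 + 20×300 = 12,150.

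Sum in 'other':
- A: 1,200 + 4,200 + 450 = 5,850.
- B: 3,000 + 2,400 + 450 = 5,850.

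Mean in both: (12,150 + 5,850)/100 = 180 mg. The mean within 'other' is also the same, 5,850/19 = 307.9 mg.

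Sum of squares in the named categories: 62,500 + 100,000 + 585,000 + 1,800,000 = 2,547,500.

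Sum of squares in 'other':
- A: 240,000 + 1,470,000 + 202,500 = 1,912,500.
- B: 750,000 + 960,000 + 202,500 = 1,912,500.

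SD in both: √[(4,460,000 − 100 × 180²)/99] = √(1,220,000/99) = 111.0 mg.

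The ordered 50th and 51st values fall among the 150 mg patients (positions 36 to 61), so the median is 150 mg. The mode is 150 mg (26 patients), the minimum 50 mg and the maximum 450 mg in both.

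| | A | B |
|---|---|---|
| All five category percentages, n, mean, median, mode, min, max, SD | same | same |
| At 200 mg | 6% | 0% |
| At 250 mg | 0% | 12% |
| Above 300 mg | 13% | 7% |

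Every dose-level statistic in Section 9.3 agrees, while the share above 300 mg is 13% in one country and 7% in the other.

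**The case against.** The best reply is that the categories are not read alone. Section 9.3 pairs them with a continuous summary, and in simple cases this is enough. Suppose one country had a fifth of its patients at 200 mg, another had a fifth above 300 mg, and the rest were identical. A reader might infer that the plan could not tell them apart. It could: the means would differ by more than 0.20 × 100 = 20 mg, and only the second country's maximum would exceed 300 mg. Nor may one infer that any 'other' share could lie anywhere from entirely below to entirely above 300 mg. A maximum of 300 mg or less puts the share above 300 mg at exactly zero, and a higher maximum rules zero out. Both replies stand. They do not reach the mixed case in step 4.

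Section 9.3 also summarises duration for each dose, and Section 9 requires the number of responses. If tabulated at every exact dose, this would show how many patients ever received 200 mg, 250 mg or more. But a patient whose dose changed appears at several doses. Ever-use counts do not give the share by initial, last or modal dose, and in general they only bound the share whose maximum exceeded 300 mg.

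Finally, exact doses are captured, and 'other' could be itemised in table shells or in an analysis plan that is not shown. That is true, so no data are lost. But Section 9.3 did not leave the categories open. It fixed a list that differs from the form, and an analysis that follows it exactly omits these proportions.

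**Conclusion.** The point holds as a reporting defect. The dose lists of Section 9.3 and Appendix B disagree, and when 'other' mixes 200 or 250 mg with doses above 300 mg, the planned statistics do not in general give the proportion in any of the three groups. The worked case proves that the proportions are not identified; it does not predict how large the loss will be.

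That size is unknown. The protocol reports only that "The proportion of patients taking Seroquel XR at various dose levels varied from 1% to 67"% in a Dutch source, without saying which doses, and gives no share at 200 mg, at 250 mg or above 300 mg. That two of six pre-printed rows are merged is a count of rows on a form and should not be read as a third of patients. If few patients fall in 'other', little is hidden. The sample size, Table 2 and data collection are unaffected.

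**What to change.** In Section 9.3, replace the category list by the questionnaire rows (50, 100, 150, 200, 250 and 300 mg/day), and split the remaining doses into above 300 mg/day and any other value. Apply it to initial, last, maximum and modal dose, by country and overall. This aligns reporting categories with the form; it says nothing about which dose is appropriate.

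The cost is one line of protocol text and the table shells. No new data are needed. The downside is some small cells, whose precision Table 2 already describes: a 6% category has a 95% interval of 1.3% to 10.7% with 100 patients and 3.7% to 8.3% with 400.
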